#### 5.3.2 Demographics and baseline characteristics

Demographic variables are

- Gender (Male, Female)
- Race
- Ethnicity
- Age in years (quantitative and qualitative variable: 18-64, 65-74, ≥75)
- Region
- Weight in kg (quantitative and qualitative variable: <50, 50-<100, ≥100 kg)

- BMI in kg/m^2 (quantitative and qualitative variable: <30, ≥30 kg/m^2)

Continuous data will be summarized using the number of available data, mean, standard deviation (SD), median, minimum, and maximum for all enrolled participants. Categorical and ordinal data will be summarized using the number and percentage of participants enrolled.

Baseline safety and efficacy parameters will be presented along with the safety and efficacy summaries.

### 5.3.3 Medical or surgical history

Medical (or surgical) history includes all the relevant medical (or surgical) history during the lifetime of the participant.

This information will be coded to a LLT, PT, HLT, HLGT, and associated primary SOC using the version of Medical Dictionary for Regulatory Activities (MedDRA) currently in effect at the time of database lock-

Comorbidity will be summarized separately. The following comorbid disease will be summarized from eCRF pages completed by investigators based on participant reporting. Asthma will be captured under disease characteristics at baseline.

Medical and surgical history will be summarized for enrolled participants and by SOC and PT, sorted by internationally agreed order of SOC and by the decreasing frequency of PT within SOC.

### 5.3.4 Disease characteristics at baseline

The following baseline disease characteristics will be summarized (see Section 5.4.1 for calculation details):

- Time since first diagnosis of nasal polyposis (years)
- Age of onset at nasal polyposis (years)
- Number of previous surgeries for nasal polyposis (0, 1, 2, ≥3)
- Number of previous surgeries for nasal polyposis by type
  - Nasal/sinus endoscopy, surgical, with ethmoidectomy, total (anterior and posterior)
  - Nasal/sinus endoscopy, surgical, with maxillary and antrostomy with removal of tissue from maxillary sinus
  - Nasal/sinus endoscopy, surgical, with frontal sinus exploration, with or without removal of tissue from frontal sinus
  - Nasal/sinus endoscopy, surgical, with maxillary antrostomy
  - Nasal/sinus endoscopy, surgical, with sphenoidotomy with removal of tissue from the sphenoid sinus
  - Nasal/sinus endoscopy, surgical, with sphenoidotomy

- Nasal/sinus endoscopy, surgical, with ethmoidectomy, partial (anterior)
- Excision, nasal polyp(s), extensive
- Excision, nasal polyp(s), simple
- Excision or destruction (eg,laser), intranasal lesion; internal approach
- Time since most recent nasal polyposis surgery (years)
- Smoking history (former, current, never)
- Cessation prior to screening (months) for former smokers
- Smoking quantity (cigarettes per day)
- Frequency of alcohol drinking in the past 12 months (never, occasional, at least monthly, as least weekly, at least daily)
- For daily drinkers, Number of standard alcohol drinks on a typical day (1 or 2, >2)
- Asthma comorbidity status (Yes, No)  
For asthma participants, the following will be provided:
  - Age at onset of asthma (Years)
  - Time since first diagnosis of asthma (years)
  - Time since last asthma exacerbation (days)
  - Number of asthma exacerbations experienced 1 year before visit 1 (comorbid asthma patients only, quantitative variable and qualitative variable: 0, 1, 2, 3, ≥4)
- Number of courses of systemic corticosteroid (SCS) use during the past 2 years (0, 1, 2, 3, 4, ≥5). A course of SCS is considered continuous if treatment is separated by less than 7 days.
- Number of days of SCS use during the past 2 years (0, >0 - ≤7, >7 - ≤14, >14 - ≤21, 21 - ≤28, >28)

Any technical details related to computation, dates, and imputations for missing dates are described in [Section 5.4.2](#).

Continuous data will be summarized using the number of available data, mean, standard deviation (SD), median, minimum, and maximum for enrolled participants. Categorical and ordinal data will be summarized using the number and percentage of enrolled participants.

### **5.3.5 Prior and concomitant medications**

All medications taken within 30 days prior to screening and until end of the study, including nasal polyposis medications, chronic rhinosinusitis medications, asthma medications, and all other medications are to be reported in the case report form (CRF) pages.

All medications will be coded using the World Health Organization-Drug Dictionary (WHO-DD) version currently in effect at the time of database lock.

Prior medications are those the participant used prior to first IMP injection. Prior medications can be discontinued before first administration or can be ongoing during treatment phase.

Concomitant medications are any treatments received by the participant concomitantly to the IMP, anytime from the first administration of IMP to the end of study. A given medication can be classified as a prior medication and a concomitant medication at the same time.

Any technical details related to computation, dates, imputation for missing dates are described in Section 5.4.4.

Medications will be summarized by treatment group according to the WHO-DD dictionary, considering the first digit of the anatomic category (ATC) class (anatomic category) and the first 3 digits of the ATC class (therapeutic category). All ATC codes corresponding to a medication will be summarized, and patients will be counted once in each ATC category (anatomic or therapeutic) linked to the medication. Therefore, patients may be counted several times for the same medication.

Medication tables will be sorted by decreasing frequency of ATC followed by all other therapeutic classes. In case of equal frequency regarding ATCs (anatomic or therapeutic categories), alphabetical order will be used. Concomitant medication received during first IMP to last IMP +14 days and concomitant medication received during first IMP to end of study will be summarized separately.

Medications will also be summarized by generic name sorted by decreasing frequency.

#### COVID-19 vaccines

The participants who received COVID-19 vaccines are summarized.

## **5.4 APPENDIX 4 DATA HANDLING CONVENTIONS**

### **5.4.1 Demographic formulas**

Age (years) = Year of informed consent - Year of birth

Age at onset of nasal polyposis (years) =  
Year of nasal polyposis diagnosis date - Year of birth

BMI (kg/m^2) = Weight (kg) / height (meters)

They all will be 18 and above per the inclusion, creatinine clearance (CLcr) value will be derived using the equation of Cockcroft and Gault:

CLcr (ml/min) =  
 $(140 - \text{age}) \times \text{weight (kg)} \times (1 - 0.15 \times \text{sex}(0-M, 1-F)) / (0.814 \times \text{creatinine } (\mu\text{mol/l}))$

CLcr will be calculated using the last weight measurement on or before the visit of the creatinine measurement and age at the lab sampling date.

Here age is calculated as following:

$$\text{Age} = \text{Year of lab sampling date} - \text{Year of birth}$$

#### 5.4.2 Disease characteristics formulas

- Time since first diagnosis of nasal polyposis (years):  
 $(\text{Year of enrollment} - \text{Year of first diagnosis of nasal polyposis}) + (\text{month of enrollment} - \text{month of first diagnosis of nasal polyposis})/12$
- Time since most recent nasal polyposis surgery (years):  
 $(\text{Year of enrollment} - \text{Year of most recent nasal surgery}) + (\text{month of enrollment} - \text{month of most recent nasal surgery})/12$
- Cessation prior to screening (months) for former smokers:  
 $(\text{Year of enrollment} - \text{Year of cessation}) \times 12 + (\text{month of enrollment} - \text{month of cessation})$
- For asthma participants, the following will be provided:
  - Time since first diagnosis of asthma (years):  
 $(\text{Year of enrollment} - \text{Year of first diagnosis of asthma}) + (\text{month of enrollment} - \text{month first diagnosis asthma})/12$
  - Times since last asthma exacerbation (days):  
 $\text{Date of enrollment} - \text{date of last asthma exacerbation}$

#### 5.4.3 Reference dates

The baseline value of efficacy parameters is defined as the last available value up to enrollment but prior to the first dose of study medication unless otherwise specified. The baseline value of safety parameters is defined as the last available value prior to the first dose of investigational medicinal product (IMP).

#### 5.4.4 Missing Data

For categorical variables, patients with missing data are not included in calculations of percentages unless otherwise specified. When relevant, the number of patients with missing data is presented.

##### *Treatment Duration when IMP end date is missing*

For the calculation of the treatment duration, the date of the last dose of IMP is equal to the date of last administration reported on the end-of-treatment case report form page. If this date is missing, the exposure duration should be left as missing.

The last dose intake should be clearly identified in the case report form and should not be approximated by the last returned package date.

### ***Medication missing/partial dates***

No imputation of medication start/end dates or times will be performed. If a medication date or time is missing or partially missing and it cannot be determined whether it was taken prior or concomitantly, it will be considered a prior and a concomitant medication.

### ***Adverse events with missing or partial date/time of onset***

Missing or partial adverse event onset dates and times will be imputed so that if the partial adverse event onset date/time information does not indicate that the adverse event started prior to treatment, the adverse event will be classified as treatment emergent. These data imputations are for categorization purpose only and will not be used in listings. No imputation is planned for date/time of adverse event resolution.

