9.3.1 General considerations

The baseline value is defined generally as the last available value before first IMP administration.

The observation period will be divided into 2 segments:

- The **pre-treatment period** is defined as the period up to first IMP administration.
- The **treatment-emergent period** is defined as the period from the first IMP administration to the last visit in the study.

Dose regimen groups in the extension term after Week 24 will be defined as follows:

- 300 mg q2w group: participants who were administered at least 1 dose of the 300 mg q2w regimen and never experienced q4w administration during the extension term after Week 24
- 300 mg q4w group: participants who were administered at least 1 dose of the 300 mg q4w regimen during the extension term after Week 24

During the treatment term, including efficacy variable after Week 24, continuous variables and binary variables for efficacy by each visit will be summarized using descriptive statistics and frequency table in both the PP and mITT populations.

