#### *Observation period*

The observation period will be divided into 2 segments:

- The **pre-treatment period** is defined as the period up to first IMP administration.
- The **treatment-emergent period** is defined as the period from the first IMP administration to the last visit in the study or the date of treatment discontinuation if discontinued from the study, whichever is earlier.

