### **4.7.2 Adverse events**

#### **General common rules for adverse events**

All safety analyses up to Week 24 will be analyzed for the SAF. Safety data collected during the extension term after Week 24 up to Week 52 will be reported for the SAFE. Safety analyses for the extension term will be presented by dose regimen group and overall.

All adverse events (AEs) will be coded to a lower-level term (LLT), preferred term (PT), high-level term (HLT), high-level group term (HLGT), and associated primary system organ class (SOC) using the latest MedDRA version currently in effect at the time of DBL.

AEs will be categorized as:

- Pre-treatment AEs: AEs that developed, worsened or became serious during the pre-treatment period.
- Treatment-emergent adverse events (TEAE)s: AEs that developed, worsened or became serious during the treatment-emergent period
- Post-treatment AEs: AEs that developed, worsened or became serious after the treatment-emergent period.

Similarly, deaths will be categorized in the pre-treatment and treatment-emergent periods.

The primary focus of AE reporting will be on TEAEs. Pre-treatment AEs will be described separately.

An AE with incomplete or missing date/time of onset will be classified as a TEAE unless there is definitive information to determine it is a pre-treatment AE.

If the assessment of the relationship to IMP is missing for an AE, this AE will be assumed as related to IMP. If severity is missing for 1 of the treatment-emergent occurrences of an AE, the severity will be imputed as the maximal severity of the other occurrences. If the severity is missing for all the occurrences, severity will be left as missing.

Multiple occurrences of the same event in the same participant will be counted only once in the tables within a treatment phase.

The AE tables will be sorted as indicated in [Table 7](#).

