**Table 8 - Analyses of adverse events**

Type of AE	MedDRA levels
Overview	
TEAE	Primary SOC, HGLT, HLT and PT Primary SOC and PT Primary SOC PT
TEAE related to IMP as per Investigator's judgment	Primary SOC, and PT
Treatment emergent SAE	Primary SOC, HGLT, HLT and PT
TEAE leading to permanent discontinuation	Primary SOC, HGLT, HLT and PT
TEAE leading to death (death as an outcome of the AE as reported by the Investigator in the AE page)	Primary SOC, HGLT, HLT and PT
TEAE by maximal intensity	Primary SOC, HGLT, HLT and PT
Pretreatment AE	Primary SOC, HGLT, HLT and PT
Post-treatment AE	Primary SOC, HGLT, HLT and PT
TEAE(s) related to COVID-19	Primary SOC, HGLT, HLT and PT
TEAE(s) occurred within 2 weeks of a COVID-19 vaccine	Primary SOC, HGLT, HLT and PT

a Will include the following AE categories: any AEs, AEs by severity, any related AEs, any serious AEs, any related serious AEs, any AEs leading to death, any AEs leading to permanent IMP discontinuation

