### 5.2 APPENDIX 2 CHANGES TO PROTOCOL-PLANNED ANALYSES

Protocol Version	Approval Date	Changes	Rationale
1	11-May-2021	4.1 GENERAL CONSIDERATIONS	This is to prevent the case that patient discontinues treatment very

Protocol Version	Approval Date	Changes	Rationale
		
Observation period
 
 
The treatment-emergent period is defined as the period from the first IMP administration to the last visit in the study or the date of treatment discontinuation if discontinued from the study, whichever is earlier.
 
	
early, but have a EOS conducted, for example, 24 weeks after the last IMP.

		
4.1 GENERAL CONSIDERATIONS
 
Rescue
 
Participants who have undergone surgery or received SCS for any reasons, <del>and/or received selected prohibited medications</del> are considered rescued. NP surgery and SCS use will be determined by the corresponding eCRF pages, <del>while selected prohibited medications will be determined based on corresponding WHODD code in EFC14280.</del>
 
The date of rescue will be the earliest date of having undergone surgery or received SCS for any reason, <del>and/or received selected prohibited medications.</del>
 
And delete "selected prohibited medications" in the sections related to changes to the above definitions.
	
For the purpose of consistency with EFC14280, it focus the following data handling.
 
 
only surgery for NP or receive SCS triggers non-responder imputation
 
rescue treatment define as undergone surgery or received SCS
 

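### For adverse events with incomplete onset dates, the SAP tests only the start of treatment, so an event known to begin after the treatment-emergent period is still counted as treatment-emergent

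*SAP*

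**What the plan says.** Two places in the SAP give the rule for incomplete onset dates.

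- SAP 5.4.4: where the partial information "does not indicate that the adverse event started prior to treatment, the adverse event will be classified as treatment emergent". The imputed dates serve only to classify: "These data imputations are for categorization purpose only and will not be used in listings". No algorithm is given.
- SAP 4.7.2: an AE whose onset is not fully known "will be classified as a TEAE unless there is definitive information to determine it is a pre-treatment AE".

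The periods to which the rule applies are set elsewhere.

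- Protocol 9.3.1: the treatment-emergent period "is defined as the period from the first IMP administration to the last visit in the study". Protocol 9.3.5.1 accordingly has two AE categories, pre-treatment and treatment-emergent.
- SAP 4.1: the period runs from first IMP "to the last visit in the study or the date of treatment discontinuation if discontinued from the study, whichever is earlier".
- SAP 4.7.2 adds a third category, "Post-treatment AEs: AEs that developed, worsened or became serious after the treatment-emergent period", and Table 8 plans a summary for it under "Post-treatment AE".
- SAP Appendix 2 logs the shortening of the period. Its stated purpose is to deal with a patient who discontinues treatment very "early, but have a EOS conducted, for example, 24 weeks after the last IMP".

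**The concern.** The date rule has one boundary and suits the protocol's two-category scheme. There, every event that did not start before treatment was treatment-emergent up to the last visit, so a test against first IMP was enough. The SAP created a second boundary, the end of the treatment-emergent period, and a category beyond it, but left the date rule unchanged. Two identical late events in a participant who stopped early are then classed differently only because one lacks a day of onset. The fully dated event is post-treatment and the partly dated one is a TEAE.

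TEAE and serious TEAE incidence up to Week 24 are secondary endpoints, and the same incidences over 52 weeks are exploratory endpoints. An event placed wrongly is counted against treatment in the very situation that the logged change was meant to exclude.

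**Working it through.** No figure in the plan depends on this rule, so the check is to apply the SAP's definitions to a case modelled on its own example.

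**Inputs**

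- Gap between last IMP and the final visit: 24 weeks (example in SAP Appendix 2).
- End of the treatment-emergent period: treatment discontinuation, if earlier than the last visit (SAP 4.1, read with Appendix 2).
- Assumed calendar: first IMP on 10 January 2022. Treatment stops 56 days later, on 7 March 2022 (Day 57); this is also taken as the last IMP date. The last visit is 24 × 7 = 168 days after that, on 22 August 2022.
- Week 24 is Day 169 (Protocol schedule), which is 27 June 2022.

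**Step 1. Compare the classes month by month.** Suppose the month and year of onset are known and the day is missing. Compare the class given by every possible full date with the class given by the rule.

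| Known onset month, 2022 | Class under possible full dates | Class under the SAP rule |
|---|---|---|
| January | pre-treatment or TEAE | TEAE |
| February | TEAE | TEAE |
| March | TEAE or post-treatment | TEAE |
| April, May, June, July, August | post-treatment only | TEAE |

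In January and March the date is ambiguous, and defaulting to TEAE is a reasonable conservative choice. In the last five months nothing is ambiguous, and the rule still returns TEAE.

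**Step 2. Sensitivity to the end date.** SAP 4.7.1 credits 14 days of exposure after the last q2w dose. Ending the period then would give 7 March + 14 days = 21 March. April to August would still lie wholly after it.

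**Step 3. Outcomes that can be affected.** April and May lie wholly before 27 June, so events in those months would enter the up-to-Week-24 TEAE tables, which carry the secondary safety endpoint. Serious TEAEs can be affected in the same way. TEAEs leading to discontinuation cannot be inflated, because an event that starts after IMP has stopped cannot have caused the stop.

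**Step 4. Size.** With 25 treated participants, one participant is 1/25 = 4 percentage points. The tables count participants with at least one event, so a row changes only if that participant has no other event counted in it.

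**Step 5. Frequency.** The planned drop-out is 20%, and 0.20 × 25 = 5 participants. This is only a rough guide to the number exposed. Some will leave without further observation, and some may stop after Week 24. An affected event also needs onset after the period and a date that is incomplete but still informative. The documents give no rate for that combination.

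**The case against.** **The default is conservative.** It over-counts harm rather than hiding it. That defence stands for ambiguous dates. It does not cover a date whose known part settles the class. The SAP's own medication rule in 5.4.4 uses its default only when the timing cannot be determined.

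**The end of the period is itself unclear.** SAP 4.1 ties the earlier end to participants who discontinued from the study. Read literally, someone who stops IMP but attends the scheduled last visit has not left the study. Their period would run to that visit, and a late event would be a TEAE even with a full date. This ambiguity is real. The rationale in Appendix 2, however, describes an early treatment stop with a much later final visit, so off-treatment events of this kind are what the change was meant to exclude.

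**The circumstances are narrow.** Protocol 7.1.1 withdraws participants from further procedures for several stopping reasons, although the same section also provides for follow-up to scheduled completion after a permanent stop. SAEs must be reported within 24 hours (Protocol 8.3.1), so a missing onset day is least likely for them. Both points limit the number of events.

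**Stronger readings that a reader might infer, and that the documents do not support:**

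- That the rule turns every AE into a TEAE. Fully dated AEs follow SAP 4.1 and 4.7.2 as intended.
- That it cancels the logged change. The change still operates for all fully dated events.
- That partly dated events have no place on either side of Week 24. If the known month settles the side, SAP 4.7.2 settles the table (SAF or SAFE). Only a month that straddles Week 24 or a wholly missing date lacks a convention, and that is missing programming detail rather than an error.

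**Conclusion.** The point holds as a limited inconsistency. For AEs with missing or partial onset dates only, the rule in SAP 4.7.2 and 5.4.4 gives the wrong class when the known part of the date lies wholly after the treatment-emergent period. It assigns TEAE where a full date would give post-treatment.

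This rests on reading the end of the period in SAP 4.1 in line with Appendix 2. It mainly concerns participants who stop IMP early and stay under observation. Few events are expected, possibly none. Each could move TEAE or serious TEAE incidence by up to 4 percentage points, assuming a denominator of 25. No efficacy result is touched. It is a worthwhile tidy-up because the correction is nearly free, but it is not a threat to the trial's conclusions.

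**What to change.** Use the same sentence in SAP 4.7.2 and 5.4.4:

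> An AE with a missing or partial onset date is classified as treatment-emergent unless the known part of the onset date (or, for pre-treatment onset, the AE end date) shows that it started before first IMP, or the known part of the onset date shows that it started after the end of the treatment-emergent period, in which case it is a post-treatment AE.

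The AE end date is limited to the first exception because it can prove onset before treatment but cannot prove onset after the period. Ambiguous dates remain TEAEs.

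In SAP 4.1, align the condition about discontinuing from the study with the Appendix 2 rationale, so that it is clear whether a participant who stops IMP but stays in the study is covered. A convention for onset dates that straddle Week 24 could be added to the programming specifications, but it is optional.

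The cost is one sentence in two sections, one clarified phrase and a small change to the date derivation. A few fewer events may be labelled treatment-emergent, but they remain visible in the post-treatment AE table already planned.
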